9.2 Eligibility

A listing of subjects not fulfilling any eligibility criteria will be created.

9.3 Demographic and Baseline Characteristics

Demographic variables include age, sex, ethnicity, and race. Age will be calculated in years relative to the informed consent date.

Other baseline characteristics include lesion counts at baseline, site type (dermatologist vs other), number of sites and a breakdown of site type, number of randomly assigned subjects in household (1 subject vs 2 subjects), number of households and breakdown of household size, age at and time since initial clinical diagnosis of the current molluscum episode and age at and time since onset of symptoms of current molluscum episode. Descriptive statistics will be presented for ages and other continuous variables. Frequency counts and percentages will be presented for sex, ethnicity, race and other categorical variables. Demographic and baseline characteristics will be summarized for the Safety, ITT, and PP Populations.

9.4 Extent of Exposure

Study drug exposure will be summarized for each treatment using the total number of applications, the duration of treatment, and the number of subjects requiring a treatment interruption and modification. Duration of treatment is defined as the last application date minus the first application date plus 1.

Study drug compliance will be summarized and calculated as follows:

Compliance [%] = (Actual applications applied)/(Planned applications) × 100, where

- Actual applications applied = Planned applications – the number of applications missed
- Planned applications = Number of applications (days) planned up to the point of treatment discontinuation or date of Week 12 visit, whichever is later.

This implies that if a subject treatment discontinues treatment prior to Week 12 due to complete clearance, then the number of applications takes this information into account and the subject is not penalized for having complete clearance.

Compliance will be further summarized into 2 groups:

1. Subjects who did not have any interruptions or modifications using the same formula as above, and
2. Subjects with modifications or interruptions. For these subjects, an adjusted compliance will be calculated in the following manner: the actual applications applied will be the same as above but the planned applications will exclude the time where the subject has dosing interrupted.

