8.5 Dose and Administration

Subjects will apply treatment once daily for up to 12 weeks to all active lesions identified at baseline and new lesions that arise during treatment. If the investigator determines all lesions are cleared at a clinic visit, the treatment may stop. If treatment is stopped due to clearance, subjects will continue regularly scheduled visits through Week 24/ET2.

An increase in the number of MC lesions (with or without inflammatory reaction) during the early treatment phase is often observed. It is important to instruct the subject/caregiver to treat the new lesions as well as the existing lesions.

Each dose will consist of berdazimer gel or vehicle gel with hydrogel thoroughly mixed together by the subject or caregiver and applied to the lesions and approximately 1 cm surrounding each lesion. Periocular lesions will be treated if the lesions are at least 2 cm from the edge of the eye. If a subject has more than 20 MC, a second dose of berdazimer gel or vehicle gel with hydrogel can be prepared to ensure appropriate coverage of all lesions.

At the investigator's discretion, the subject may be placed on a drug holiday for up to 2 weeks at a time in the event of a significant local skin reaction (LSR). This will be captured in the electronic data capture (EDC) system and the subject's diary. The investigator should instruct the subject how long to hold study drug and the planned date to re-start treatment. Site staff should contact the subject on the day of the planned re-start and assess whether the LSR has resolved enough to resume treatment. If it has not resolved sufficiently, the drug holiday may be extended as long as the entire extension has not exceeded 2 weeks. If the LSR flares after re-introduction of study drug, the study drug should be permanently discontinued and the EDC system updated appropriately. Please see [Section 7.2.4](#) for additional information.

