8.6 Accountability

The dispensing and return of all study drug will be recorded on a dispensing log. The subject number/initials, and the initials and date of the person dispensing and receiving the returned medication will be documented on this form. All study product will be weighed at the time it is dispensed and when it is returned. The tube weights will be recorded in the electronic case report form (eCRF).

Inventory records must be readily available for inspection by the trial monitor and/or auditor, and open to government inspection at any time.

Study drug returned by subjects at will be held on site until accountability has been completed. The site will be instructed on return or destruction of used and unused clinical supplies.

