8.8 Compliance

Subjects will be provided a diary to record doses. Review of subject compliance will be conducted at each visit and missed doses recorded on the subject diary will be recorded on the eCRF.

No reconciliation will be performed on the diary compliance against the tube weights. Subject compliance will be based on calculation from the missed doses recorded from the subject diary only.

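### Compliance is planned minus diary-recorded missed doses, so planned days without diary data are credited as applied

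*Combined protocol and SAP*

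**What the plan says.** The final SAP, Section 9.4 Extent of Exposure, defines compliance as actual over planned applications, times 100. Its two terms are:

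- Numerator: "Actual applications applied = Planned applications – the number of applications missed".
- Denominator: "Planned applications = Number of applications (days) planned up to the point of treatment discontinuation or date of Week 12 visit, whichever is later".

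Protocol Section 8.8 Compliance fixes the source of the missed count: "Subject compliance will be based on calculation from the missed doses recorded from the subject diary only". What reaches the database is likewise limited to misses, since "missed doses recorded on the subject diary will be recorded on the eCRF". The same section adds: "No reconciliation will be performed on the diary compliance against the tube weights". Section 8.6 nevertheless has all product weighed at dispensing and return, with the weights entered in the eCRF.

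Table 1 of the protocol has diaries collected at Weeks 2, 4, 8 and 12. The SAP's missing-data rules do not reach this case: Section 10.4 covers missing response and Appendix B covers missing dates.

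**The concern.** A numerator obtained by subtraction treats absence of information as evidence of dosing. Each planned day without diary data goes into the denominator, and nothing is available to take it out of the numerator. The error runs one way: a lost diary can raise the reported value above what was applied, but cannot lower it. One lost diary can hide 14 or 28 days, given the collection visits.

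What is at stake is interpretation. Apart from visit days, dosing is at home by the subject or caregiver for up to 12 weeks. If the trial shows no difference, a reader will want to know whether the gel was applied. Table 14.1.3.2 is the plan's only compliance summary, and it would not show how much of its value rests on recorded information.

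**Working it through.** The documents state no compliance figure, so there is nothing to reproduce. The check applies the SAP formula to simple cases.

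**Inputs**
- Formula: 100 × (planned − missed) / planned (final SAP, Section 9.4).
- Planned days: 84 = 12 weeks × 7, from once-daily dosing for up to 12 weeks (protocol Section 8.5). Counting the Week 12 in-clinic dose would make it 85, which changes little.
- Diary periods: 14, 14, 28 and 28 days (protocol Table 1).
- Assumption: an absent diary contributes zero missed doses.

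**Case 1. Diaries for the first 28 days with 4 misses, none after, planned period running to Day 84**
- As written: (84 − 4)/84 = 80/84 = 95.2%.
- Documented days only: (28 − 4)/28 = 24/28 = 85.7%, with 84 − 28 = 56 days unknown.
- If all 56 unknown days were in fact missed: 24/84 = 28.6%. If all were applied: 80/84 = 95.2%.

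The formula as written therefore returns the upper limit of what the data allow.

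**Case 2. No diary at all**
- As written: (84 − 0)/84 = 100%, whatever was applied.

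**Case 3. Same adherence throughout, later diaries not returned**

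| Adherence | Days without diary | As written | Documented days only | Unknown days counted as missed |
|---|---|---|---|---|
| 50% | 28 | (84 − 28)/84 = 66.7% | 50.0% | 28/84 = 33.3% |
| 50% | 56 | (84 − 14)/84 = 83.3% | 50.0% | 14/84 = 16.7% |
| 80% | 28 | (84 − 11.2)/84 = 86.7% | 80.0% | 44.8/84 = 53.3% |
| 80% | 56 | (84 − 5.6)/84 = 93.3% | 80.0% | 22.4/84 = 26.7% |

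Each undocumented day is worth 1/84 = 1.2 percentage points, credited as if dosed.

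**Case 4. Treatment discontinuation dated Day 28, no Week 12 visit, 4 misses recorded**
- Planned period ends at Day 28: (28 − 4)/28 = 85.7%. There is no inflation.

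The problem thus needs a planned period that continues while the diary does not.

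**The case against.** The strongest reply is that no text says an absent diary means zero missed doses. If the programmer leaves the count missing, compliance is missing and the 100% never appears. The annotated eCRF, the data management plan and the derived-dataset specifications might settle this, and none is available here. That stands as a limit on the figures. It does not remove the point: the written rule subtracts only recorded misses, and a choice that moves a subject from 100% to no value belongs in the SAP.

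Four stronger readings are tempting and not supported:

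- *Subjects lost to follow-up get the highest values.* Loss to follow-up is a recorded reason for stopping treatment (protocol Section 6.3.1), and without a Week 12 visit the planned period ends at discontinuation, as in Case 4.
- *Subjects who lose diaries are the least adherent.* This is plausible, but the documents give no evidence for it.
- *Safety conclusions are distorted.* The plan has no exposure-adjusted safety analysis; Section 13.1 reports subject incidence.
- *The no-reconciliation sentence must be removed.* It rules out reconciling the diary with the weights, not summarizing the weights. Removing it would change the protocol, which under Section 15 needs an amendment and IRB approval. Weight is also a weak check: Sections 8.1.1 and 8.5 let the amount used vary with lesion number, including a second preparation above 20 lesions.

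It is also fair to say that restricting to documented days assumes the unknown days resemble the known ones. If they were worse, the value would still be too high, which is why diary coverage has to be reported beside it.

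**Conclusion.** The point holds as a minor defect in a descriptive summary. For subjects whose planned period continues but whose diary is not returned or is incomplete, the formula credits undocumented days as applied and can only err upward. In the illustration the gap is 95.2 − 85.7 = 9.5 percentage points, and the value reaches 100% with no diary. These figures rest on 84 planned days and on an absent diary being entered as zero misses. How many subjects would be affected cannot be known from the documents.

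The reach is the compliance table, and the total number of applications in Section 9.4 if derived the same way, which the SAP does not state. The primary ITT analysis does not use compliance. Low compliance is not a named deviation for the PP population in Section 9.5, although that list is open and the exclusion criteria are left to the data review meeting.

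**What to change.** In SAP Section 9.4:

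1. Calculate compliance over planned days covered by a returned diary, and say how blank days within a returned diary are treated.
2. Set compliance to missing for a subject with no returned diary.
3. Report by arm the number of subjects without diary data and the share of planned days not covered.
4. State how the total number of applications is derived.

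This still bases compliance on diary-recorded misses, so protocol Section 8.8 can stay as it is, including its sentence on reconciliation. Optionally, add a descriptive by-arm summary of the tube weights already in the eCRF, labelled as supportive only because use depends on lesion number.

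The cost is a few lines of SAP text and one or two added summary rows. Stated compliance may be lower, some subjects will have no value, and diary-return dates must be available in the database.

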6.3 Discontinuation

6.3.1 *Treatment Discontinuation*

If at any time during the study the investigator determines that it is not in the best interest of the subject to continue treatment, the subject's treatment will be discontinued. The investigator can discontinue the treatment for a subject at any time if medically necessary. If a subject's treatment is permanently discontinued by the investigator because of an AE, that AE should be indicated as the reason for treatment discontinuation. In this case, the subject is discontinued from the treatment, but still participates in the study and the subject is encouraged to follow the visit schedule and complete all assessments.

In addition, the investigator may instruct the subject to temporarily halt treatment of a specified region (i.e., due to an adverse event). This treatment modification and the reason for the temporary drug interruption should be documented in the subject's source documents and eCRF. The lesions in the impacted area should continue to be counted in the lesion count during the period of treatment modification.

The investigator may discontinue a subject's treatment if the subject/caregiver has failed to follow study procedures or to keep follow-up appointments. Appropriate documentation in the subject's study record and the study database regarding the reason for treatment discontinuation must be completed.

Reasons for an investigator's withdrawal of a subject **from the treatment** may include, but are not limited to, the following:

- Safety (e.g., severe adverse reactions, pregnancy)

- When a concomitant medication or treatment likely to interfere with the results of the study is reported, or required, by the subject, the investigator will decide, in consultation with the CRO whether the subject is to be withdrawn.

Reason(s) for discontinuation from the treatment as listed in the study record will be entered into the study database as follows:

- Completed (complete clearance prior to Week 12)
- Adverse Event (including LSRs deemed to be significant by investigator)
- Withdrawal by Subject/Caregiver
- Physician Decision
- Protocol Violation
- Lost to Follow-Up
- Pregnancy
- Lack of Efficacy
- Worsening of Molluscum Contagiosum
- Other

6.3.2 *Study Discontinuation*

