9.4 Extent of Exposure

Study drug exposure will be summarized for each treatment using the total number of applications, the duration of treatment, and the number of subjects requiring a treatment interruption and modification. Duration of treatment is defined as the last application date minus the first application date plus 1.

Study drug compliance will be summarized and calculated as follows:

Compliance [%] = (Actual applications applied)/(Planned applications) × 100, where

- Actual applications applied = Planned applications – the number of applications missed
- Planned applications = Number of applications (days) planned up to the point of treatment discontinuation.

This implies that if a subject treatment discontinues treatment prior to Week 12 due to complete clearance, then the number of applications takes this information into account and the subject is not penalized for having complete clearance.

Compliance will be further summarized into 2 groups:

1. Subjects who did not have any interruptions or modifications using the same formula as above, and
2. Subjects with modifications or interruptions. For these subjects, an adjusted compliance will be calculated in the following manner: the actual applications applied will be the same as above but the planned applications will exclude the time where the subject has dosing interrupted.

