4. STUDY DESIGN AND PLAN

This is a Phase 3 multi-center, randomized, double-blind, vehicle-controlled, parallel group study to be conducted in approximately 340 subjects ≥ 6 months of age with MC. After obtaining informed consent/assent, subjects who satisfy entry criteria will be randomized to a 2:1 (active:vehicle) scheme. Subjects receiving current treatment for MC at the time of the Screening Visit will enter a washout period of up to 14 days prior to randomization. In the event no washout period is required, Screening and Baseline visit activities may be combined into a single visit. At randomization, subjects will be stratified into 4 strata corresponding to the cross-classification of household number of randomly assigned subjects (1 subject per household vs 2 subjects per household) and investigator type (dermatologist vs other). Households randomizing 2 subjects will receive the same treatment assignment for both subjects. Up to 2 subjects from the same household may be randomly assigned on the same day, if both individually meet all inclusion and exclusion criteria. For subjects in the same household, Screening can occur on different days; however, the baseline visit must occur on the same day.

Subjects or their caregivers will apply SB206 12% or Vehicle Gel QD for a minimum of 4 weeks and up to 12 weeks to all lesions identified at Baseline and new treatable lesions that arise during the course of the study. Subjects or their caregivers will continue to treat the area until the next scheduled visit even if the lesion(s) clear. If the investigator determines all lesions are cleared at a clinic visit, the treatment may stop. At Weeks 2, 4, 8 and 12, the investigator will count and record the number of active (raised, treatable) molluscum lesions per body area. At Weeks 2, 4,

and 8, the investigator will determine if new lesions have occurred since the last visit, and the subject or caregiver will be instructed by the investigator to re-initiate treatment. If treatment is stopped due to clearance, subjects will continue regularly scheduled visits through Week 24.

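### SAP 9.4 counts planned applications to the later of treatment stop and the Week 12 visit, so an early stop for clearance is ignored although the next sentence says it is allowed for.

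*Combined protocol and SAP*

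**What the plan says.** The file holds three SAP versions. The latest is the one that cites TLF shells Version 3.0. Its section 9.4 defines compliance as actual over planned applications, with these two parts:

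- Denominator: "Planned applications = Number of applications (days) planned up to the point of treatment discontinuation or date of Week 12 visit, whichever is later".
- Numerator: "Actual applications applied = Planned applications – the number of applications missed".

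It then draws a consequence for subjects who stop before Week 12 because they are clear: "the number of applications takes this information into account and the subject is not penalized for having complete clearance".

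In the two earlier SAP versions the denominator ended at the stop: "Planned applications = Number of applications (days) planned up to the point of treatment discontinuation". The same explanatory sentence followed.

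Three other provisions matter:

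- **Attendance after a clearance stop (SAP section 4):** "If treatment is stopped due to clearance, subjects will continue regularly scheduled visits through Week 24".
- **Attendance after an investigator's stop for an adverse event (protocol 6.3.1):** the subject "still participates in the study and the subject is encouraged to follow the visit schedule".
- **Source of missed doses (protocol 8.8):** "Subject compliance will be based on calculation from the missed doses recorded from the subject diary only".

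**The concern.** For a subject who stops early and attends Week 12, the later of the two dates is always the Week 12 visit, so the stop date has no effect on the denominator. The explanatory sentence followed from the earlier definition. It does not follow from the current one, which added the Week 12 clause and left the sentence unchanged.

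The stop date will rarely be used at all. No study drug is provided after the Week 12 visit, and protocol 6.2.7 calls the dose given there the final one, so a stop should not fall after an attended Week 12 visit.

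At stake is the accuracy of the compliance table (14.1.3.2) and the compliance listing (16.2.5.4). Total applications, part of the exposure summary, is also at risk if it is derived by the same formula. Appendix C requires two independently programmed datasets to match, but that check will not find the error if both programmers follow the literal text.

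**Working it through.** The plan states no compliance figure to reproduce, so the check applies the 9.4 formula to example subjects.

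**Inputs**

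- Week 4 is Day 29, Week 8 is Day 57 and Week 12 is Day 85, each ±5 days (protocol 6.2.5 to 6.2.7).
- Assumed: one application per day from Day 1 through the stop day *s*, and a Week 12 visit on Day W = 85.
- Assumed: the number *m* of doses missed before the stop. The documents give none, so 0, 5 and 7 are shown.
- Assumed: an adverse-event stop on Day 20 with 6 missed doses and later attendance at Week 12.

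**Formulas**

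- Counted to the stop: (s − m)/s.
- As written, days after the stop not logged as missed: (W − m)/W.
- As written, days after the stop logged as missed: (s − m)/W.

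| Stop | Missed | Counted to stop | As written, not logged | As written, logged |
|---|---|---|---|---|
| Day 29, clear | 0 | 29/29 = 100% | 85/85 = 100% | 29/85 = 34.1% |
| Day 29, clear | 5 | 24/29 = 82.8% | 80/85 = 94.1% | 24/85 = 28.2% |
| Day 29, clear | 7 | 22/29 = 75.9% | 78/85 = 91.8% | 22/85 = 25.9% |
| Day 57, clear | 0 | 57/57 = 100% | 85/85 = 100% | 57/85 = 67.1% |
| Day 57, clear | 5 | 52/57 = 91.2% | 80/85 = 94.1% | 52/85 = 61.2% |
| Day 57, clear | 7 | 50/57 = 87.7% | 78/85 = 91.8% | 50/85 = 58.8% |
| Day 20, AE | 6 | 14/20 = 70.0% | 79/85 = 92.9% | 14/85 = 16.5% |

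**Not logged.** Compliance is overstated by m(1/s − 1/W). For s = 29 and m = 7 that is 7 × (1/29 − 1/85) = 15.9 percentage points. With m = 0 the percentage is right, but the application count is still too high by W − s: 85 − 29 = 56 for a Day 29 stop and 85 − 57 = 28 for a Day 57 stop.

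**Logged.** Compliance is multiplied by s/W: 29/85 = 0.341 or 57/85 = 0.671. This is the penalty the SAP says it avoids.

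**Visit window.** With Week 12 anywhere from Day 80 to Day 90, the logged figure with no missed dose runs from 29/90 = 32.2% to 29/80 = 36.25% for a Day 29 stop, and from 57/90 = 63.3% to 57/80 = 71.25% for a Day 57 stop.

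**Related gap in adjusted compliance.** For subjects with interruptions, 9.4 removes the interrupted days from the denominator and keeps the same numerator. It does not say whether those days enter the missed count. Of a drug holiday, protocol 8.5 says "This will be captured in the electronic data capture (EDC) system" and the diary, but not that it is recorded as missed doses. Take a 14-day hold, no other missed dose and treatment to Day 85, so that the adjusted denominator is 85 − 14 = 71. If hold days are logged as missed, the result is 71/71 = 100%. If not, it is 85/71 = 119.7%.

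**The case against.** **A cleared subject may not be penalised.** Someone told to stop has no dose due and so none to miss, and missed doses come from the diary alone. On that reading a cleared subject with no missed doses scores 100%. This is the likelier reading, and it makes the very low percentages the less likely branch. It does not rescue the rule: the application count still ignores the stop, and anyone with real missed doses has them diluted over days with no treatment. One could also say that nothing is planned after a clearance stop, but then the added clause does nothing for these subjects, and the text does not say so.

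**The explanatory sentence covers clearance only.** Running the denominator to Week 12 for other early stoppers might be deliberate. The contradiction in wording is indeed confined to clearance stops. Stops for adverse events still suffer the same distortion, because the numerator is built from the denominator and credits applications that were never made.

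**Suspected allergic contact dermatitis.** These subjects also continue visits, so excluding them from the problem could be questioned. Their Week 12/ET1 assessments are done at discontinuation (protocol 7.2.4 and 7.2.5), and SAP section 7 treats such a form as Week 12 when no Study Exit form has the same date. On that mapping they are unaffected.

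**Adjusted compliance has a natural reading.** Keeping the numerator makes most sense if hold days are already counted as missed, which gives 100%. That is fair: this part needs clarifying but is not an error in itself.

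**Compliance is descriptive.** It is not a model covariate, a planned test or a listed example of a significant deviation, and treatment duration has its own definition from first and last application dates. All of that stands and limits the consequence.

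**Conclusion.** The concern holds. The current definition contradicts the sentence that explains it, and it gives a wrong application count, a wrong percentage or both for any subject who stops early and later has a Week 12 visit. In the examples with missed doses, the percentage is 2.9 (94.1 − 91.2) to 22.9 (92.9 − 70.0) points too high if days after the stop are unlogged. If they are logged, it is 28.9 (87.7 − 58.8) to 65.9 (100 − 34.1) points too low across all examples. These sizes rest on the assumed stop days, missed-dose counts and a Day 85 visit.

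Subjects with no Week 12 visit after the stop are not affected. The documents give no rate of early stopping by arm, so neither the number affected nor any imbalance between arms can be calculated. The effect is on descriptive reporting only; the primary ITT analysis, alpha and power do not change. It should be corrected, because the compliance table can otherwise be badly wrong for individual subjects.

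**What to change.** In SAP 9.4, replace later with earlier in the definition of planned applications, or restore the earlier versions' definition ending at treatment discontinuation. Add that days after permanent discontinuation count neither as planned nor as missed.

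Two clarifications belong in the same edit:

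- **Re-start after a clearance stop:** take the last permanent stop as the discontinuation date, and count the days between stop and re-start neither as planned nor as missed.
- **Adjusted compliance:** remove interruption days from both the planned and the missed counts, so that the figure cannot exceed 100%.

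The cost is one word and two or three sentences. The main correction uses the diary and the recorded stop date. The clarifications also need hold and re-start dates. Protocol 8.5 provides for recording drug holidays, but the provisions cited here do not say where a re-start after clearance is recorded, so the data source for that rule should be confirmed.
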